7.4.2. Objectives

1.1 Identify & describe current ERM practice in UK PICs

1.2 Assess capability of UK PICs to deliver ERM

7.5. Data collection/analysis:

The survey will be designed and piloted by the PERMIT co-applicant study team. It will be distributed via established networks of known lead clinicians (Paediatric Intensive Care Society – Study Group, PICU physiotherapy and occupational therapy networks). We anticipate >75% return rate following previous practice surveys. Numeric and textual data will be analysed using descriptive statistics and framework analysis respectively.

7.5.1. Target population:

We plan to sample at least 3 lead health care practitioners (1 allied health, 1 medical and 1 nursing) from all 28 UK and Irish PICs (total number of participants n=84). We will also approach other health care professionals and therapists at individual PICs if the original three responders are unable to answer questions (e.g. regarding service provision of occupational therapy or dietitians).

List of planned NHS and Irish PICUs.

- 1 Addenbrooke's Hospital, Cambridge
- 2 Noah's Ark Children's Hospital for Wales, Cardiff
- 3 Royal Manchester Children's Hospital
- 4 Great Ormond Street Hospital, London (PICU/NICU)
- 5 Evelina London Children's Hospital
- 6 King's College Hospital, London
- 7 Leeds General Infirmary
- 8 Freeman Hospital, Newcastle upon Tyne
- 9 Great North Children's Hospital, Newcastle upon Tyne
- 10 Royal Stoke University Hospital
- 11 Queen's Medical Centre, Nottingham
- 12 John Radcliffe Hospital, Oxford
- 13 Royal Brompton Hospital, London
- 14 Alder Hey Children's Hospital, Liverpool
- 15 Sheffield Children's Hospital
- 16 Southampton Children's Hospital
- 17 St George's Hospital, London
- 18 St Mary's Hospital, London
- 19 Birmingham Children's Hospital
- 20 Bristol Royal Hospital for Children
- 21 Glenfield Hospital, Leicester
- 22 Leicester Royal Infirmary
- 23 Royal Hospital for Sick Children, Edinburgh
- 24 The Royal London Hospital
- 25 Royal Hospital for Children, Glasgow
- 26 Royal Belfast Hospital for Sick Children
- 27 Our Lady's Children's Hospital, Crumlin, Dublin
- 28 Temple Street Children's University Hospital, Dublin

7.5.2. Recruitment

Senior health care practitioners will be identified through the Paediatric Intensive Care Society, physiotherapy and occupational health membership lists. Permission for distributing to the email list will be obtained from the Chair or Vice Chairman of the Paediatric Intensive Care Study Group. Emails will be sent out by the Paediatric Intensive Care Society directly and the PERMIT researchers will not have access to participants' individual emails. The survey will be sent out with an introductory email (*PERMIT_Study_Survey_Invite v2.0 31JAN2019*) and a PIS (*PERMIT_Survey_PIS Version 2.0 31/01/2019*). Reminders will be sent out a further two times, at weekly intervals. The reminders will be sent to all original invitees (surveys will be completed anonymously so there will be no way of knowing who has already completed the survey). Those who have already completed the survey will be asked not to complete it again.

7.5.3. Consent

Potential participants will be sent an introductory email (*PERMIT_Study_Survey_Invite v2.0 31JAN2019*) containing an introduction to the aims and objectives of the PERMIT study survey, explicitly stating that completion of the survey is optional, but that completion and submission implies informed consent. A more detailed PIS (*PERMIT_Survey_PIS v2.0 31012019*) will be attached to this email, which potential participants will be encouraged to read.

7.5.4. Participant feedback

Participants will be invited to take part in future aspects of the PERMIT study (focus groups).

We will also publish the results of the PERMIT study survey as part of the full HTA project report and associated published manuscripts and this will be available to all participants to read. Links will be provided via the Paediatric Intensive Care Society mailing list.

In the invitation email and patient information sheet, the participants are informed of their right to decline participation or to withdraw before the survey is submitted. Once they have submitted their answers they will not be able to withdraw from the questionnaire study and this is detailed in the PIS and at the beginning of the survey.

As the survey results will be anonymous it will not be possible to remove a participant's data after the survey has been submitted. This information is clearly outlined in the PIS (*PERMIT_Survey_PIS v2.0 31012019*)

7.6. Data protection

7.6.1. Confidentiality

Completed surveys will be submitted anonymously. If participants choose to give their contact details in order to take part in a future focus group, these will not be linked to their completed questionnaire.

All information collected about participants during the study will be treated confidential, and will be handled, stored and destroyed in accordance with the Data Protection Act 2018.

Data will be stored securely with [SmartSurvey] while the survey is ongoing, and will be stored securely on the University of Birmingham server once data collection is complete.

Survey answers will be kept for 10 years after the end of the PERMIT study. If contact details are provided, these will be deleted within 6 months of the end of the study.

7.6.2. Storage and access to data

Survey answers will be stored securely on SmartSurvey until the data collection period is complete. Responses will then be exported to spreadsheets and stored securely on University of Birmingham servers. Only [name] will have access to this SmartSurvey account.

All co-investigators and research students under [name] supervision will have access to anonymised data once exported.

Data will be deleted from SmartSurvey once data collection is complete and data has been exported to University of Birmingham servers. In accordance with the data will be securely deleted from University of Birmingham servers after the end of the PERMIT study + 10 years

7.6.3. Optional contact details obtained from survey participants – identifiable

Participants' details will be stored securely on SmartSurvey until the data collection period is complete. Participants details will then exported to password protected spreadsheets and stored securely on University of Birmingham servers.

Deleted from SmartSurvey once data collection complete and data has been exported to University of Birmingham servers. Securely deleted from University of Birmingham servers

7.7. Significance/ benefits

This important piece of work is a key component of the larger PERMIT feasibility study and will inform the design and feasibility of future research into ERM in paediatric critical care. Importantly it will improve our understanding of current practice and provision of ERM in the UK and guide the development of a future intervention trial of ERM in critically ill children.

7.8. Risks

This survey poses no risk to research staff or participants.

The study involves the sharing of contact information for involvement in future components of the PERMIT study. Provision of this contact information is optional and data storage procedures as outlined above and in the Patient Information leaflet will minimise risk of data breach and ensure compliance to GDPR regulations.

7.9. Ethics approval

The University of Birmingham granted institutional ethical approval on 05/02/2019, Sponsor reference ERN_18-1134. Consent was implied through survey completion.

PHASE 1b PROTOCOL: Observational Study

8. PHASE 1b: OBSERVATIONAL STUDY PROTOCOL

8.2. Trial Summary

Title	Paediatric Early Rehabilitation/Mobilisation during InTensive care feasibility Observational study
Short Title	PERMIT Observational study
Sponsor Name and Reference	University of Birmingham REF ERN_18-1134
Funder Name and Reference	NIHR HTA 17/21/06
Study Design	Observational cohort study
Overall Aim	To prepare for a definitive ERM trial, we will: i) Identify current ERM practice, and ii) Establish the patient population for whom ERM may be appropriate
Study Objectives	1.1 Identify & describe current ERM practice in UK PICUs 1.2 Assess capability of UK PICUs to deliver ERM 1.3 Establish and model how many/which CYP would be appropriate for ERM in the PIC population
Population & Inclusion Criteria	Inclusion: All Children and Young Persons (CYP) (0-<16 years) Admitted to PICU Remain within PICU on day 3 post-admission Exclusion: Local decision by PI or treating clinical team not to include patient Parent or guardian chooses to opt-out
Study Centres	14 UK NHS PICUs: 1. Addenbrooke's Cambridge 2. Alder Hey Children's NHS Foundation Trust 3. Birmingham Children's Hospital 4. Evelina London Children's Hospital 5. Freeman Hospital, Newcastle upon Tyne Hospitals NHS Foundation Trust 6. GOSH CICU and GOSH PICU, Great Ormond Street Hospital for Children NHS Foundation Trust 7. Great North Children's Hospital, Newcastle 8. Nottingham Children's Hospital 9. Oxford University Hospitals 10. Royal Hospital for Children Glasgow

	
 11. Royal Manchester Children's Hospital 12. Southampton Children's Hospital, Southampton General Hospital 13. St Mary's Hospital, Imperial London 14. University Hospital Leicester and Glenfield Hospital, Leicester 15. King's College Hospital NHS Foundation Trust, London 16. Leeds Children's Hospital, Leeds General Infirmary 17. The Royal Hospital for Children and Young People, Edinburgh (RHCYP)
Follow up duration	7 days
Definition of End of study	Final report 24 months after commencement
Planned study period	24 months

Figure 2 PERMIT Observational study flow chart

8.3. List of Abbreviations

CRF: Case report form

CV: Curriculum Vitae

CYP: Children and young persons

DoB: Date of birth

HQIP: Healthcare Quality Improvement Partnership

ICH-GCP: International Conference on Harmonisation of Technical Requirements for Registration of Pharmaceuticals for Human Use – Good Clinical Practice

NICU: Neonatal Intensive Care Unit

PCCMDS: Paediatric critical care minimum dataset – data provided to PICANet

PICANet: Paediatric Intensive Care Audit Network (PICANet)

PICU: Paediatric Intensive Care Unit

PIS: Patient Information Sheet

REC: Regional Ethics Committee

REDCAP: Research Electronic Data Capture

SOP: Standard Operating Procedure

8.4. Trial Rationale

8.4.1. Justification for participant population

Observation of infants and children in PICU who may receive early rehabilitation and mobilisation (ERM) interventions as part of standard care.

8.4.2. Justification for design

Observational study to observe staff performing ERM interventions within PICU will provide real-world data that would inform aspects of the study. The observational approach of this design, combined with the use of routine data will reduce the burden of data collection for PERMIT and minimise the impact on parents and families during a difficult time.

8.5. Aims, Objectives and Outcome Measures

8.5.1. Aims and Objectives

Aims:

- Identify current ERM practice,
- Using routinely collected data, establish the patient population for whom ERM may be feasible.

Objectives:

- Identify & describe current ERM practice in UK PICUs
- Assess the capability of UK PICUs to deliver ERM
- Establish and model how many/which CYP may be suitable for ERM in the PICU population using routinely collected data.

8.6. PERMIT observational study Outcome Measures

8.6.1. Primary outcome

- Prevalence of delivery of ERM on day 3 post PICU admission.

8.6.2. Primary outcome assessment

- The prevalence and scope of ERM will be described as the proportion of patients with any 'active interaction' delivered on day 3 post-admission.

8.6.3. Secondary outcomes

- Prevalence and incidence of ERM delivery between day 3 and day 10 post PICU admission, quantification of ERM delivered per patient, characteristics of patients receiving ERM, type of ERM interventions delivered, and factors associated with variability of delivery between PICUs.

8.6.4. Secondary outcome assessment

- Cumulative prevalence for each day in PICU after day 3, up to day 10 post-admission with whom ERM may/may not be considered appropriate.
- Quantification of dose (duration, measured in minutes) of ERM on each day and characteristics of patients receiving ERM will be presented using standard descriptive statistics.
- Further analysis will be undertaken to understand factors associated with ERM and the incidence of ERM.
 - Multilevel multivariable logistic regression models with random effects for PICU site will be used to evaluate predictors of ERM provided on day 3. Predictors of interest will be established following the Phase 1a survey and expert group consensus (examples include: age, presence of PICU protocol, diagnostic category, sedation level and PIM3 probability of mortality score).
- To calculate incidence rates and incidence rate ratios for number of ERM interventions, accounting for variable length of PICU stay, we will use a multilevel multivariable Poisson Model.

8.7. Study Design and Setting

This is an observational study to ascertain current practice, identifying current ERM practices within the PICU settings and barriers/facilitators to ERM delivery.

We plan to directly observe current ERM practices within UK PICUs, identify patients who do and do not receive ERM, describe variation between PICUs and factors associated with ERM practices.

Following the observation of current ERM delivery and identification of patients who may benefit from ERM in selected PICs, we will use this information to model how many patients may be available in the UK for a potential future RCT. This will be achieved by comparing and modelling the patient demographic information with the existing full PICANet dataset.

8.8. Target population/setting:

8.8.1. Inclusion:

- All Children and Young Persons (CYP) (0-<16 years)
- Admitted to PICU
- Remain within PICU on day 3 post-admission

8.8.2. Exclusion:

- Local decision by PI or treating clinical team not to include patient
- Parents or guardians choose to opt-out.

The broad inclusion criteria will allow observation of all types of patients admitted for PICU care (acute and elective e.g. post-surgical recovery) and all age ranges without the requirement for 48hrs ventilatory. (23)

8.8.3. Sampling of sites

We will purposely select 14 UK PICUs of three varying sizes (n=6 large: >800 admissions/year, n=5 medium: 500-800 admissions/year, n=3 small: <500 admissions/year) with varying activity level of ERM practice (e.g. high, low users) identified from PERMIT survey responses.

8.8.4. Patient identification and screening

Local sites will screen all current patients daily at 09:00 within their PICU for eligibility to participate in PERMIT study over a 14 day observation period. When patients become eligible then case report forms (CRF) will be completed for each patient and each active ERM interaction performed. (See data collection)

8.8.5. Recruitment/enrolment:

All eligible patients will be included in PERMIT observational study unless parents/guardians choose to opt-out of data sharing (see consent).

8.8.6. Strategies to maximise recruitment

Daily screening by local research staff of patients will identify eligible patients and patients becoming eligible the following day. Each participating site will have a designated research co-ordinator to identify patients and collect data on delivered ERM activities by clinical staff.

8.9. Outcomes

8.9.1. Primary outcome:

- The prevalence and scope of ERM will be described as the proportion of patients with any 'active interaction' provided on day 3 post-admission.

8.9.2. Secondary outcomes:

- Cumulative prevalence for each day in PICU after day 3, up to day 10 post-admission will be calculated.
- Quantification of doses of ERM on each day and characteristics of patients receiving ERM will be presented using standard descriptive statistics.
- Further analysis will be undertaken to understand factors associated with ERM and the incidence of ERM.
 - Multilevel multivariable logistic regression models with random effects for PICU site will be used to evaluate predictors of ERM provided on day 3. Predictors of interest will be decided by expert group consensus (examples include: age, presence of PICU protocol, diagnostic category, sedation level and PIM3 probability of mortality score).
- To calculate incidence rates and incidence rate ratios for number of ERM interventions, accounting for variable length of PICU stay, we will use a multilevel multivariable Poisson Model.

8.10. Data collection

To maximise efficiency and ensure we can estimate point prevalence, all study sites will recruit and collect data over the same 21 day observation period (either in November 2019 or January 2020). Patients will be recruited through the first two weeks of the PERMIT study period (e.g. study day 1 to 14) with a further week to complete follow up (study day 15-21). Individual patient data collection and observations will occur for up to 7 days after patients are eligible and recruited or until PICU discharge, whichever is sooner (e.g. data collection commenced day 3 post-admission and continued up to day 10 post-admission).

8.10.1. Unit level data

Data will be collected on each study day (1-21) at a unit level to record the following

[figure not shown]
- Number of staff available in PICU (divided by grade and speciality) at 09:00.
- Census of the number of patients in the PICU at 09:00.
- Number of beds open to admissions at 09:00.
- Nursing number to patient ratio at 09:00.

8.10.2. Patient-level data

Two categories of patient-level data will be collected.

- 1) Routine PICANet data which include the PCCMDS (Paediatric critical care minimum data set).
- 2) PERMIT study observational data (new data).

Figure 3: Screening and data collection schema for individual patients

Day 0 = day of admission. Day 1 = 1st day at 9.00. CRF = Case Report Form. PICANet = Paediatric Intensive Care Audit Network

8.10.3. PICANET routinely collected data

Participating sites already collect PICANet defined data items and submit to PICANet web. For patients included in the PERMIT study, local sites will collate the PICANet data already collected for that patient and combine this data with the PERMIT observational data below. This data will be pseudo-anonymised at the local site prior to secure transfer to the PERMIT trials office.

Currently, all patients admitted to PICU have data recorded via the Paediatric Intensive Care Audit Network (PICANet). PICANet has permission to collect patient identifiable data under section 251 of the NHS Act 2006 (originally enacted under Section 60 of the Health and Social Care Act 2001). We will use the PICANet data to supplement and reduce the burden of data collection for PERMIT. Patient characteristics (e.g. reason for admission, severity of illness score (e.g. PIM3 (43)), critical care interventions) and individual patient PIC resource use (mechanical ventilation days, renal replacement therapy, vasoactive drug use). A full list of data items and data definitions can be found at www.picanet.org.uk/documentation.

8.10.4. PERMIT observational study patient level data

Figure 3: Screening and data collection schema for individual patients displays the daily planned data collection for individual patients.

From Day 3 of PICU admission onwards, until the patient is discharged from PICU (or day 10 of admission, whichever is sooner), patient-level data will be collected for the PERMIT study.

1) Clinical status

This will include health care interventions, ventilator requirement, sedation and coma level, presence of delirium, inotropic support and neuromuscular blocking drug usage. This data will supplement routinely collected PICANet data. Data will be collected twice, between 09:00 and 10:00 and between 14:00 and 15:00 each day.

2) Observed ERM active interaction

We will undertake a behavioural mapping procedure (44) to capture 'active interaction' versus 'no interaction' with a patient in a therapeutic rehabilitation context after local researcher training, and piloting of observation case report form. Frequency, quantity, and type of 'active interaction' of ERM delivered by physiotherapy, occupational therapy, speech & language, play, psychology, nurse and parent will be recorded.

Clinical staff performing the activity will be instructed to record planned activity and delivered activity duration in medical records. A research nurse will use this data to complete active interaction CRF.

CRFs will be collated hourly between 9 am and 5 pm by the local site research nurse. 'Active ERM interaction/interventions' will be defined using the PERMIT logic model (**Error! Reference source not found.**) and based on paediatric modification of published ICU mobility scales. (45)

With the addition of free-text for any activity performed outside of the standardized mobility scales.

This data will be recorded on the "Observed ERM active interaction" CRF.

3) Summary of overnight ERM activities

Daily at 09:00 researchers will retrospectively review the clinical case records to record any ERM activities that occurred overnight. Overnight is defined as the time from the end of Observed active interaction period 17:01, until 08:59 prior to the start of the next Observed active interaction period.

This data will be recorded on the *Summary of overnight ERM activities* CRF.

8.11. Sample Size

We aim for a sample size of n=150 CYP. Accepting our hypothesis that there is wide variability in the current prevalence of ERM delivery across PICUs (e.g. 20%-80%: (reference: personal communication with Glasgow, Nottingham, Birmingham, Southampton PIC clinicians) we anticipate identifying any ERM use in 75/150 patients (prevalence of 50%). With 150 participants a confidence interval with a width of 8% either side of the estimate (41.7%-58.3) can be produced. This degree of accuracy is adequate for our purposes.

8.12. Future RCT Sample Size Modelling:

Using the primary outcome of the prevalence of ERM, PICU and patients characteristics, we will subsequently use the UK PICANet database to identify and count potential trial population sample size using national anonymised data for all UK and Irish PICUs. Anonymised PICANet data has been used efficiently for previous NIHR HTA funded PIC RCTs (FEVER study: HTA [15/44/01](#), *CHiP study*: HTA 05/506/03). Using PICANet admission data, on average 20,000 patients are admitted per year across 28 PICUs (averaging 2 patients/unit/day). Of these 40-45% of patients stay on PICU for ≥3 days (20% > 7 days), on average 5.5 to 6 patients/unit/week will be eligible. Enrolling patients admitted over a 14-day recruitment window in 14 units, 150 patients will be included (average n=11 patients/PICU/14 days). (1)

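### The ±8-point precision in section 8.11 holds only for 150 independent children; with the between-PICU spread assumed in the same paragraph it is roughly ±9 to ±13 points for UK PICUs

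*Protocol*

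**What the plan says.** The primary outcome of the observational study is the proportion of children with any active ERM interaction on day 3 (Protocol sections 8.6.1, 8.6.2 and 8.9.1). Section 8.11 sets the sample size: "We aim for a sample size of n=150 CYP". It starts from "wide variability in the current prevalence of ERM delivery across PICUs (e.g. 20%-80" per cent), a range attributed to clinicians at four centres, and continues: "we anticipate identifying any ERM use in 75/150 patients (prevalence of 50" per cent). It then states the precision, "With 150 participants a confidence interval with a width of 8% either side of the estimate (41.7%-58.3) can be produced", and calls it adequate.

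Section 8.12 gives the structure of the sample: "Enrolling patients admitted over a 14-day recruitment window in 14 units, 150 patients will be included (average n=11 patients/PICU/14 days"). Section 8.8.3 says how the units are found: "We will purposely select 14 UK PICUs of three varying sizes", with a mix of high and low ERM users.

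Section 8.24.1 plans random PICU effects for the model of predictors and a multilevel Poisson model for the number of interventions. For the primary prevalence it says only that a proportion will be described.

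The summary in 8.2 also announces 14 PICUs, but its list runs to "17. The Royal Hospital for Children and Young People, Edinburgh (RHCYP").

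**The concern.** Children in the same unit share that unit's practice. If unit prevalences differ as widely as 8.11 supposes, 150 children from 14 units carry less information about UK prevalence than 150 independent children. The paragraph assumes strong clustering and then quotes a precision that requires none.

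The figure is the only precision argument offered for n=150, and it concerns the primary outcome. The objectives in 8.5.1 are about UK PICUs, and 8.12 carries the primary outcome forward to a count over all UK and Irish units. A reader who takes ±8 points at face value would think the national prevalence better known than this design can make it.

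**Working it through.** **Inputs from the protocol.** n = 150, expected prevalence p = 0.50, unit range about 20% to 80% (8.11); k = 14 units, so m = 150/14 = 10.71 children per unit (8.12); 28 UK and Irish PICUs (7.5.1, 8.12).

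**Assumptions.** A two-sided 95% level, which 8.11 does not state but which reproduces its limits. The protocol gives no ICC or between-unit SD, so several readings of the 20% to 80% range are shown.

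**Step 1: the printed figure.** The exact (Clopper-Pearson) interval for 75/150 is 41.74% to 58.26%, which rounds to the printed limits. The simple normal half-width is 1.96 × √(0.25/150) = 8.0 points. Both treat the 150 children as independent, so the printed interval contains no allowance for unit.

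**Step 2: allowing for unit.**

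- ICC = SD² / [p(1 − p)] = SD² / 0.25
- Design effect DE = 1 + (m − 1) × ICC = 1 + 9.71 × ICC
- Half-width = 1.96 × √(0.25 × DE / 150), or with t on 13 df in place of 1.96
- With a finite-population correction (FPC) for 14 of 28 units: 1.96 × √[ (SD²/14) × (1 − 14/28) + (0.25 − SD²)/150 ]

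Half-widths are in percentage points, with the t version in brackets:

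| Reading of 20%-80% | SD | ICC | DE | Effective n | No FPC | With FPC |
|---|---|---|---|---|---|---|
| ±3 SD | 0.100 | 0.04 | 1.39 | 108 | 9.4 (10.4) | 8.7 (9.6) |
| ±2 SD | 0.150 | 0.09 | 1.87 | 80 | 11.0 (12.1) | 9.4 (10.4) |
| Uniform | 0.173 | 0.12 | 2.17 | 69 | 11.8 (13.0) | 9.9 (10.9) |
| Half the units at each end | 0.300 | 0.36 | 4.50 | 33 | 17.0 (18.7) | 12.8 (14.1) |

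Worked example for the uniform reading: SD² = 0.60²/12 = 0.03; ICC = 0.03/0.25 = 0.12; DE = 1 + 9.71 × 0.12 = 2.17; half-width = 8.0 × √2.17 = 11.8.

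**Step 3: inference to the selected units only.** Dropping the between-unit term leaves 1.96 × √[(0.25 − SD²)/150], about ±7.5 to ±7.6 for ICC 0.12 to 0.09. On that footing ±8 is, if anything, slightly cautious.

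**Step 4: number of units.** Holding n at 150 but spreading it over 17 units gives ±10.4 to ±11.1 (±11.3 to ±12.1 with t) for ICC 0.09 to 0.12 without FPC. With FPC for 17 of 28 it gives ±8.8 to ±9.1 (±9.6 to ±9.9 with t).

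**The case against.** - **The size is uncertain in both directions.** The 20% to 80% range is offered as an example and rests on personal communication; every ICC above is inferred from it. A reader might take ±11 to ±13 as a floor, with anything wider equally likely. The protocol does not support that: the ±3 SD reading or the finite-population correction each brings the half-width below ±10. The ±17 case needs half the units at each extreme and should not be used as an expectation. If the study opened 17 to 19 units at 11 children each (187 to 209 children), the corrected half-width for ICC 0.09 to 0.12 would be 7.5 to 8.5 points (8.1 to 9.2 with t), close to the printed figure, though from more children than planned. This objection stands, and is why a range is given.

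- **No interval method is fixed for the analysis.** A reader might infer that the reported interval will be too narrow. The protocol says only that a proportion will be described, and the interval method may be set out in a statistical analysis plan that is not shown. The criticism is therefore confined to the planning statement in 8.11.

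- **Sites are chosen purposively.** Design-effect formulas and finite-population corrections assume randomly drawn units. Deliberate spreading over size and ERM activity could reduce the between-unit contribution or add bias. This stands too: the figures are approximate, and no interval covers selection bias.

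- **The practical consequence is limited.** Section 13.8 reports the fieldwork as done, no decision rule uses ±8, and no step of the PICANet count is shown to use the interval width. That lowers the severity but does not make the statement right.

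- **The unit count may be no error of design.** Section 5.2 records an amendment adding sites, and 13.8 reports 14 units. The mismatch in 8.2 does not show that 14 is wrong, only that the passages disagree.

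**Conclusion.** The point holds. The arithmetic in 8.11 is correct for independent children; what fails is the independence assumption, which the same paragraph contradicts. At 14 units and 150 children, every reading considered that treats the PICUs as a sample gives a half-width above ±8. For ICC 0.09 to 0.12 it is ±11 to ±12 points (±12 to ±13 with t on 13 df) when units are taken as drawn from a large population. It is about ±9.4 to ±10 (±10.4 to ±11 with t) with a correction for 14 of 28 units, or with ICC 0.04 and no correction. Combining the mild spread with the correction gives ±8.7.

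These figures assume p = 0.5, a 95% level, equal unit sizes and units behaving like a random sample. Limited to the selected units, ±8 is sound, but that does not match the stated aim of describing UK PICUs. This is a should-fix point about a design assumption.

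**What to change.** 1. Keep n=150. In 8.11, either restate the expected precision as roughly ±9 to ±13 points, showing the assumed ICC and whether a finite-population correction is used, or say plainly that ±8 applies only to the sampled units.
2. Report the primary prevalence with an interval that accounts for PICU. Suitable choices are a cluster-robust interval with t on (units − 1) df, or the marginal prevalence from a random-intercept logistic model of the kind already planned for the predictors. Add that purposive site selection may introduce bias that no interval covers.
3. Separately, reconcile the 14 units in 8.2, 8.8.3 and 8.12 with the 17 entries in 8.2 (two of which name two units) and with the 14 reported in 13.8, and use the agreed number in the precision statement.

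The cost is a few sentences and about one line of analysis code. No further children are needed. The stated precision becomes less favourable.
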